2.4.4 Sensitivity analyses

No sensitivity analysis is planned.

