6.4 Treatment blinding

There is no blinding, the study is open-label to participants, investigator staff, persons performing the assessments, and the Novartis team. Furthermore, the stopping rules (Section 12.6) will be assessed by the sponsor team based on real time unblinded safety and efficacy data.

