12.4.2 Statistical model, hypothesis, and method of analysis

The efficacy analysis at Month 12 evaluates whether at least one of the two CFZ533 treatment arms meets the pre-defined success criterion.

The number of participants with composite efficacy failure is assumed to follow a binomial distribution, i.e., $r_i \sim \text{Binomial}(n_i, \theta_i)$, where r_i is the number of participants with composite efficacy failure in treatment group i, n_i is the number of participants in treatment group *i* and θ_i is the probability of composite efficacy failure.

A CFZ533 arm is considered successful if the composite efficacy failure rate difference between this CFZ533 arm and the control arm is less than 15% with probability >80%:

$$P(\theta_{\text{CFZ533}} - \theta_{\text{control}} < 0.15 | \text{data}) > 0.8.$$

The required posterior probabilities will be estimated from simulations of the posterior distributions of $\theta_{CFZ533} - \theta_{control}$ and compared to the threshold for level of proof. The prior distributions will be assumed to be non-informative. The posterior mean composite efficacy failure rates for each treatment arm and for the difference in mean response rates between CFZ533 treatment arms and control will be presented together with 95% credible intervals.

Novartis	Confidential	Page 112 of 136
Amended Clinical Trial Protocol (Version No.	04 clean)	Protocol No. CCFZ533A2202

The posterior probability of the primary decisions rule will be derived and in addition posterior probabilities of the composite efficacy failure rates for each treatment arm and the treatment difference being above various thresholds such as 10%, 15%, and 20% will also be presented.

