12.4.3 Handling of missing values not related to intercurrent event

The primary analysis is based on the FAS, i.e., all observations whether on- or off-treatment. Since participants continue to be followed after early study drug discontinuation, the number of missing values is expected to be limited. Any participant who is lost to follow-up or does not attend the Month 12 visit after treatment discontinuation will be counted as failure. A lost-to-follow-up participant is one who did not experience BPAR, graft loss, or death and whose last day of contact is prior to the day of the lower limit of the (Month 12) visit window.

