12.7 Sample size calculation

The sample size justification considers the probability of success of the study based on the success criterion for the planned sample size. The success criterion for one CFZ533 treatment arm (see Section 12.4.2) is reached if

$$P(\theta_{\text{CFZ533}} - \theta_{\text{control}} < 0.15 | \text{data}) > 0.8,$$

[figure not shown]
where θ is the composite efficacy failure rates, and the prior is Beta(1/3, 1/3).

Table 12-2 and Figure 12-2 show the probability of success of the study for a sample size of 48 participants in the CFZ533 arm and 32 participants in the control arm for a range of underlying event rates for composite efficacy failure and serious infections in the CFZ533 treatment arm and in the control arm. A control rate of 10% at Month 12 is expected based on (Levitsky et al 2016), which examined a large registry of deceased donor liver transplant participants from Scientific Registry of Transplant Recipients (SRTR) and internal Novartis studies (RAD001 Study H2304 and AEB071 Study B2203).

Table 12-2 Probability of success under different event rates for 48 participants of CFZ533 arm and 32 participants of control arm		
θ_{CFZ533}	$ heta_{ ext{control}}$	Probability of success
0.07	0.070	0.971
0.07	0.103	0.986
0.07	0.135	0.993

Novartis	Confidential	Page 121 of 136
Amended Clinical Trial	Protocol (Version No. 04 clean)	Protocol No. CCFZ533A2202
0.07	0.168	0.997
0.07	0.200	0.999
0.11	0.070	0.833
0.11	0.103	0.904
0.11	0.135	0.947
0.11	0.168	0.973
0.11	0.200	0.987
0.15	0.070	0.594
0.15	0.103	0.729
0.15	0.135	0.830
0.15	0.168	0.900
0.15	0.200	0.944

The primary analysis of renal function is based on the FAS. Participants continue to be followed after study drug discontinuation and participants with graft loss or death will have their Month 12 values imputed as described in Section 12.5.2.1. For treatment comparisons, there will be a randomized sample of 48 and 32 participants in the CFZ533 and control arms respectively after 12 months. Assuming a common standard deviation of 16 mL/min and one-sided α =0.10, there is 63, 73, or 81% power to detection a difference of 6, 7, or 8 mL/min/1.73m² respectively. If the standard deviation is 20, there is 51, 59, or 67% power respectively.

13 Ethical considerations and administrative procedures

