2.4 Analysis of the primary objective

The primary objective is to evaluate the rate of composite efficacy failure (BPAR, graft loss, or death) with CFZ533 600 mg and 300 mg Q2W maintenance regimen compared to TAC Control at Month 12 post-transplantation. Analysis will be on the FAS.

The analysis of the primary objective has been modified due to the early termination of the study.

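### The SAP's primary success rule runs on a Poisson model that stops at treatment discontinuation, and is never run on all follow-up as the stated treatment-policy estimand requires

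*SAP*

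**What the plan says.** **Protocol.** Section 12.4.2: "The number of participants with composite efficacy failure is assumed to follow a binomial distribution". A CFZ533 arm succeeds if its failure rate exceeds control by "less than 15% with probability >80" per cent. Section 12.4.3: "The primary analysis is based on the FAS, i.e., all observations whether on- or off-treatment". The same section counts as failures participants who are lost, or who miss the Month 12 visit after stopping treatment. Section 12.7 gives the probability of success for a "sample size of 48 participants in the CFZ533 arm and 32 participants in the control arm", with a Beta(1/3, 1/3) prior.

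A Poisson model appears in Section 12.4.4 as supportive, and in Section 4.5 as the interim model. In the 12.4.4 formula, follow-up ends at the Month 12 window or at loss to follow-up. Treatment stop is not a term in it.

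**SAP.** Section 1 says the study was terminated in September 2022 after the interim analysis. Section 2.4: "The analysis of the primary objective has been modified due to the early termination of the study".

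- 2.4.1 states a treatment-policy estimand, covering treatment discontinuation and loss to follow-up.
- 2.4.2 makes Poisson primary, on on-treatment time. Follow-up is the earliest of the Month 12 window end, treatment discontinuation and loss, with a Gamma(0.001, 0.001) prior on the rate and the same 0.15 and 0.8 thresholds.
- 2.4.3 ends follow-up at drug discontinuation or loss and censors participants without an event by then.
- 2.4.4: "No sensitivity analysis is planned".
- 2.4.5 keeps Kaplan-Meier failure rates to last contact, with a 95% interval for the difference, and summaries of the composite and its components. Section 5.4.2 mentions simple-proportion tables.
- 3.2 still justifies the sample size with the Beta(1/3, 1/3) rule.
- Section 4, on changes to protocol-specified analyses, is marked as not applicable.

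**The concern.** The SAP declares one estimand and analyses another. Under treatment policy, a rejection, graft loss or death after study drug stops is a failure of the assigned regimen. Under 2.4.2 and 2.4.3 that participant is censored at treatment stop. Losses to follow-up, which are failures in the protocol, are also censored.

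Termination left some participants short of 12 months, so an exposure-adjusted model is reasonable. But follow-up can be adjusted to last contact without discarding off-treatment events that were collected. With no second run of the rule, the report would state success or failure without showing whether the call depends on the change.

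**Working it through.** **1. The protocol's own figures.** Posterior for each arm: Beta(1/3 + y, 1/3 + n − y). Success if P(θ_CFZ533 − θ_control < 0.15 | data) > 0.8, weighted over all binomial outcomes for 48 vs 32. All 15 stated probabilities reproduce to within 0.001. For example, 0.11 vs 0.103 gives 0.904 (stated 0.904) and 0.15 vs 0.103 gives 0.7295 (stated 0.729).

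**2. Where the protocol rule turns.** With 3/32 control failures, the posterior probability is 0.866 at 8/48 CFZ533 failures, 0.789 at 9/48 and 0.696 at 10/48. Eight is the most that still succeeds.

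**3. One dataset, two rules.** Control: 3/32. CFZ533: 6 on-treatment failures, 4 participants with an off-treatment failure or loss, and 38 event-free. Assumed: discontinuation at 4 months, on-treatment events at 3 months. The Month 12 window ends on Day 358 (SAP 5.1), and 358/365.25 = 0.980 years.

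- *Protocol rule:* 10/48 vs 3/32 gives 0.696. Not successful.
- *SAP rule, formula as written (time does not stop at the event):* CFZ533 time = 44 × 0.980 + 4 × 0.333 = 44.5 years; control = 32 × 0.980 = 31.4 years. With λ ~ Gamma(0.001 + y, 0.001 + t), y = 6 and 3, and θ = 1 − exp(−λ), the probability is 0.958. Successful.
- *SAP rule, time stopping at the event:* CFZ533 = 38 × 0.980 + 6 × 0.25 + 4 × 0.333 = 40.1 years; control = 29 × 0.980 + 3 × 0.25 = 29.2 years. The probability is 0.936. Successful.
- *Poisson counting all 10 as events:* 0.63 to 0.76, depending on whether time stops at the event. Not successful. This applies if all four are observed failures; losses would be censored.

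With 8 on-treatment plus 2 off-treatment or lost, the protocol rule again gives 0.696 and the SAP model 0.81 to 0.88. So the calls still differ.

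**4. How often.** The documents give no discontinuation rates. Simulation used 1,500 trials per row and assumed that 25% of those who stop are lost. Assumed annual failure risk after stopping is 20% in the 10/10 and 20/10 rows and 30% in the rows with 30% stopping.

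| True on-treatment risk, CFZ533 / control | Stopping, CFZ533 / control | Protocol rule succeeds | SAP rule succeeds | SAP only | Protocol only |
|---|---|---|---|---|---|
| 0.15 / 0.103 | 0 / 0 | 0.739 | 0.730 | 0.002 | 0.011 |
| 0.15 / 0.103 | 10% / 10% | 0.721 | 0.723 | 0.062 | 0.060 |
| 0.15 / 0.103 | 20% / 10% | 0.601 | 0.711 | 0.153 | 0.043 |
| 0.15 / 0.103 | 30% / 10% | 0.434 | 0.698 | 0.283 | 0.019 |
| 0.15 / 0.103 | 30% / 30% | 0.678 | 0.681 | 0.114 | 0.111 |
| 0.25 / 0.10 | 30% / 10% | 0.114 | 0.201 | 0.110 | 0.023 |
| 0.25 / 0.10 | 30% / 30% | 0.330 | 0.222 | 0.053 | 0.161 |

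**5. What Kaplan-Meier adds.** By simple proportions against 3/32, the upper 95% limit for the difference is about 19% at 7/48 (protocol success) and about 27% at 10/48 (protocol non-success). Both exceed 15%, so the interval alone does not separate the calls.

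**The case against.** **The divergence would be visible.** A reader might infer that a success existing only under the new model would go unseen. The documents do not support that. Kaplan-Meier to last contact keeps off-treatment events, and composite and component summaries are planned. A careful reader could approximate the rule as Φ((0.15 − d)/SE), with d the difference and SE the interval width divided by 3.92. For complete follow-up against 3/32, this gives 0.850, 0.769 and 0.675 at 8, 9 and 10 failures, the same calls as the exact 0.866, 0.789 and 0.696. What remains is that the plan does not run the rule itself on these data, and that Kaplan-Meier censors losses the protocol counts as failures.

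**The model was not new.** A reader might also infer that it was chosen because the results were known, since "There is no blinding, the study is open-label to participants, investigator staff, persons performing the assessments, and the Novartis team". That cannot be shown. Poisson was pre-specified as supportive and for the interim. Protocol 12.4.4 already defines drug-discontinuation dates, and SAP 2.13 uses on-treatment data at the interim. SAP section 1 refers to an original SAP and Amendments 1 and 2, which are not available here, so the date of the on-treatment cut is unknown. What is new against the protocol is the promotion to primary and the discontinuation term in the follow-up formula.

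**The stakes are lower.** Development in this disease area had stopped and the report is abbreviated. This limits the consequences but does not align the analysis with its estimand.

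**Conclusion.** The point holds as a mismatch between the stated estimand and the primary analysis, with the protocol's rule dropped and the change not declared in section 4. The two rules can give opposite calls on plausible data: about 0.70 against 0.94 to 0.96 in the worked case, which rests on the assumed event and discontinuation times.

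The frequency is not a property of the documents. In the table, SAP-only success is 0.2% with no discontinuation and up to 28% when 30% stop on CFZ533 and 10% on control. With equal 30% stopping, disagreement runs both ways.

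A reader might take this as proof that the new model inflates success; that does not follow. At true risks of 25% and 10% with complete follow-up, the protocol's own rule succeeds with probability 0.217. The SAP rule's 0.201 in the 30%/10% row is no higher. The protocol figure falls to 0.114 there because the assumed off-treatment failures and losses enlarge the difference it measures.

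This should be corrected, but it does not invalidate the trial's conclusions.

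**What to change.** Replace SAP 2.4.4 with two analyses using the same rule, P(difference < 0.15) > 0.8:

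1. The Poisson model with events and time counted to last contact or Month 12, regardless of treatment stop. This matches the estimand in 2.4.1.
2. The protocol 12.4.2 Beta-binomial, with the 12.4.3 failure rule for losses, in full-analysis-set participants randomized early enough for 12 months' potential follow-up before termination. Label it as a restricted version of the protocol analysis.

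The second is feasible. The Amendment 04 rationale reports 59 randomized by 28 February 2021, about 18 months before termination. At 2:3:3 that is roughly 59 × 3/8 = 22 per CFZ533 arm and 59 × 2/8 = 15 controls, plus anyone randomized later with 12 months available. It is smaller than planned, so the probabilities in SAP Table 3-2 would not apply to it.

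Also label the current 2.4.2 model as on-treatment, and list the change and its reason in SAP section 4.

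Cost: two extra model runs on existing data and a few lines of text. The sponsor may have to report a less favourable success statement.

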2.4.5 Supplementary analyses

Kaplan-Meier (KM) estimates of events rates of composite efficacy failure and BPAR censored at Month 12 will be respectively summarized and presented graphically. In addition, participants who have not experienced composite efficacy failure, are lost to follow-up, or do not attend the Month 12 visit after treatment discontinuation will be censored with the censoring time defined by the last contact day.

For Kaplan-Meier estimates, Greenwood's formula will be used to estimate the variance and to derive 2-sided 95% Z-test based confidence intervals for the difference between a CFZ533 arm and the Control arm. The confidence interval will be constructed as:

$$(r_{T_i} - r_C) \pm Z_{\alpha/2} * SE_{d_i},$$

where

 r_{T_i} = Kaplan-Meier estimate of the failure rate for CFZ533 arm up to 12 months, i = 1, 2,

 r_c = Kaplan-Meier estimate of the failure rate for the control arm up to 12 months,

$$SE_{d_i} = \sqrt{SE_{T_i}^2 + SE_C^2}, i = 1, 2,$$

 SE_{T_i} = Estimated standard error for CFZ533 arm based on Greenwood's formula, i = 1, 2,

 SE_c = Estimated standard error for the control arm based on Greenwood's formula, and $\alpha = 0.05$.

Summaries of the composite efficacy failure and its individual components will be provided. Acute rejection events will be summarized by treatment and severity for central and local assessment, respectively. Histological evidence and pathological assessment of liver allograft biopsies will be provided in the listings for central and local assessment, respectively.

2.5 Analysis of the key secondary objective

2.5.1 Key secondary endpoint

The key secondary objective is to evaluate renal function (eGFR) at Month 12. GFR will be estimated using the MDRD formula (Levey et al 2006):

$$GFR [mL/min/1.73m^{2}] = 175 * (C^{-1.154}) * (A^{-0.203}) * G * R,$$

where

C is the serum concentration of creatinine [mg/dL],

A is age [years],

G = 0.742 when gender is **female**, otherwise G = 1, and

R = 1.212 when race is **black**, otherwise R = 1.

Central laboratory serum creatinine values will be used for all renal function data analysis. Summary statistics for central eGFR change from randomization will be produced.

The estimand is:

- Population: defined through appropriate inclusion/exclusion criteria to reflect the targeted population.
- Endpoint: change from randomization in eGFR at 12 months post-transplant
- Treatment of interest: the randomized treatment, CFZ533 300mg + MMF, and CFZ533 600mg + MMF, TAC+MMF, regardless of treatment or study discontinuation, loss to follow-up, ascites-based dosing adjustment, or administration of CS (treatment policy).
- Summary measure: the difference in mean eGFR on CFZ533 arms at 12 months posttransplantation as compared to control.

The mean change for each arm will be obtained through covariate-adjusted treatment effects using MMRM where visit is treated as a categorical variable. The model will contain treatment arm, visit, treatment arm*visit interaction, and eGFR at randomization with unstructured covariance matrix. In case of a convergence issue with the MMRM model, Compound Symmetry structure will be used for the covariance matrix. If convergence issue still persists,

Novartis	For business use only	Page 24
SAP		CCFZ533A2202

an ANCOVA model will be used for Month 12 visit. The estimand will be evaluated in the FAS population by comparing the difference in mean change between each CFZ533 arm and control.

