2.5.2 Statistical hypothesis, model, and method of analysis

The objective is to demonstrate that either CFZ533 treatment arm is superior to the control arm with respect to mean change in eGFR at 12 months post-transplantation.

The null hypothesis is that the mean change from randomization in eGFR for a CFZ533 treatment arm is not superior to that in the control arm.

The alternative hypothesis is that the mean change from randomization in eGFR for a CFZ533 treatment arm is superior to that in the control arm.

The null hypothesis will be tested at a significance level of 10% against a one-sided alternative hypothesis, and the test statistic will be the estimated treatment difference at Month 12 based on least squares means from either the MMRM to allow for adjustment for correlations between time points within participants or the ANCOVA model in case of convergence issue.

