2.5.3 Handling of missing values/censoring/discontinuations

The primary analysis is based on the FAS. Since participants continue to be followed after early study drug discontinuation, the number of missing values is expected to be limited. In case of missing values,

- 1. For participants with death, a value of 0 will be imputed after the time of death.
- 2. Participants that are lost to follow-up or have missing assessments will have missing values assessed via MMRM assuming MAR.

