3.3 Power for key secondary variable

The primary analysis of renal function is based on the FAS. Participants continue to be followed after study drug discontinuation and participants with graft loss or death will have their Month 12 values imputed as described in Section 2.5.3. For treatment comparisons, there will be a

Novartis	For business use only	Page 35
SAP		CCFZ533A2202

randomized sample of 48 and 32 participants in the CFZ533 and control arms respectively after 12 months. Assuming a common standard deviation of 16 mL/min and one-sided $\alpha = 0.10$, there is 63, 73, or 81% power to detect a difference of 6, 7, or 8 mL/min/1.73m² respectively. If the standard deviation is 20, there is 51, 59, or 67% power respectively. The power calcuation is completed by nQuery 8.4 based on two-sample *t*-test with equal variance.

4 Change to protocol specified analyses

Not applicable.

5 Appendix

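### If the unstructured MMRM fails, the compound-symmetry fallback may understate the Month 12 eGFR standard error, because zeros imputed after death add most variance at that visit

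*SAP*

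**What the plan says.** SAP 2.5.1 models change in eGFR with an MMRM containing arm, visit, arm by visit and eGFR at randomization, with an unstructured covariance matrix. The first fallback is: "In case of a convergence issue with the MMRM model, Compound Symmetry structure will be used for the covariance matrix". A Month 12 ANCOVA follows only if that model fails too. Neither document names a structure with visit-specific variances or an empirical (sandwich) standard error.

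On missing values, SAP 2.5.3 states that for participants who die "a value of 0 will be imputed after the time of death". Protocol 12.5.2.1 applies the same rule to graft loss as well as death. SAP 3.3 still refers to 2.5.3 as if it covered both.

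The test is on the Month 12 difference (SAP 2.5.2): "The null hypothesis will be tested at a significance level of 10% against a one-sided alternative hypothesis". That section describes the statistic as coming from the MMRM or, on a convergence problem, from ANCOVA. It does not mention compound symmetry.

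**The concern.** Homogeneous compound symmetry assumes the same variance at every visit and the same correlation between every pair of visits. The imputation rule works against this. Once a participant dies, every later visit carries a zero, so the proportion of zeros can only rise and is highest at Month 12, the tested visit. A zero lies far below the surviving values, so each one adds a great deal of variance. Compound symmetry averages the large late variance with the smaller early ones and uses that average for the Month 12 standard error.

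Compound symmetry has only two covariance parameters and rarely fails to converge. In practice the ANCOVA step behind it would almost never be reached. If the Month 12 standard error is too small, the one-sided 10% test is liberal and the intervals are too narrow.

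**Working it through.** **The plan's own figure.** SAP 3.3 takes a "randomized sample of 48 and 32 participants in the CFZ533 and control arms respectively", with the assumption "Assuming a common standard deviation of 16 mL/min and one-sided" 10% error. SE = 16 × √(1/48 + 1/32) = 3.65. The exact non-central t (78 df) gives power of 63.8, 73.4 and 81.5% for differences of 6, 7 and 8. With SD 20 it gives 51.0, 59.6 and 67.8%. The SAP states "there is 63, 73, or 81% power to detect a difference of 6, 7, or 8" and "If the standard deviation is 20, there is 51, 59, or 67% power respectively". The figures reproduce to within one point. They rest on one common SD and contain no term for zeros.

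**Inputs for the check.**
- From the documents: n = 48 and 32; SD 16, with 20 as the alternative; one-sided 10%.
- Visits: the safety-laboratory row of Protocol Table 8-1 shows ten marks from Day 15 to Month 12. The columns are broken in the text, so the days are assumed to be 15, 29, 57, 85, 113, 141, 169, 225, 281 and 337.
- Assumed, because the documents do not give them: mean eGFR m = 65; deaths by Month 12 d = 2, 4 or 6%, accruing evenly from Day 8; the same rate in each arm; otherwise complete data.
- The imputed value is read as eGFR = 0, so a participant who has died sits m below the survivors.

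**Formulas.** With p_t the proportion dead at visit t and s the survivor SD:
- Variance at visit t: V_t = (1 − p_t)s² + p_t(1 − p_t)m²
- Ratio of compound-symmetry SE to correct SE: R = √(mean of V_t over visits / V at Month 12)
- Actual one-sided error: 1 − Φ(1.2816 × R)

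**Worked case, d = 4%.** At Month 12, V = 0.96 × 256 + 0.04 × 0.96 × 4225 = 245.8 + 162.2 = 408.0. Across the ten visits V_t is 259.4, 266.1, 279.5, 292.8, 306.0, 319.1, 332.1, 357.8, 383.1 and 408.0, with mean 320.4. R = √(320.4/408.0) = 0.886. In SE terms, compound symmetry reports √320.4 × 0.2282 = 4.08 where √408.0 × 0.2282 = 4.61 is correct. Error = 1 − Φ(1.136) = 12.8%.

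**All cases, R (one-sided error):**

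| Assumption | 2% deaths | 4% deaths | 6% deaths |
|---|---|---|---|
| SD 16, even timing | 0.93 (11.7%) | 0.89 (12.8%) | 0.86 (13.6%) |
| SD 20, even timing | 0.95 (11.1%) | 0.92 (11.9%) | 0.90 (12.6%) |
| SD 16, all deaths evenly within 112 days of Day 8 | 0.97 (10.7%) | 0.95 (11.2%) | 0.94 (11.5%) |
| Survivor SD falling linearly from 1.3 × 16 to 16 | 1.08 (8.4%) | 1.01 (9.7%) | 0.97 (10.7%) |

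Milder front-loading lies between the first and third rows. With no deaths and constant SD, R = 1. If survivor SD instead rises from 10 to 16 in equal steps per visit, R is 0.82 and the error 14.6% even without deaths.

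**Cross-check by simulation.** The SAP mean model was fitted to 4,000 null trials per scenario (32/48/48, ten visits, SD 16, correlation 0.6). Mean eGFR at randomization was 75 with SD 22, so the zeros weigh more than above. With evenly spread deaths, compound symmetry gave R = 0.89 and error 13.3% at 2% deaths, and 0.83 and 15.0% at 5%. At 5% deaths R was 0.83 with correlation 0.3 and 0.8 as well. Month 12 ANCOVA stayed at 10–11% throughout. If the change score, not eGFR, is set to 0, R is 1.00. Monte Carlo error is about √(0.1 × 0.9/4000) = 0.5 points.

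**The case against.** A reader might infer that the planned Month 12 test is liberal, or that this fallback is likely to be used. The documents support neither.

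- **The trigger is not shown.** Ten visits give 10 × 11/2 = 55 covariance parameters, against at least 128 planned participants. SAP 2.5.3 expects few missing values, and the imputed zeros fill the rows of those who die. Follow-up truncated by early termination could make failure more likely, but the complete-data figures above would then not carry over exactly.
- **The direction is not guaranteed.** The documents give no variance profile over visits. If survivor variance falls after the early post-transplant weeks, compound symmetry can be conservative, as the fourth row shows.
- **The size rests on undocumented inputs.** Even timing is only one choice. Protocol 4.1 places the concern about death and graft loss in the immediate post-transplant period, part of which precedes randomization.
- **A sound fallback is already present.** The dispute is about the order of pre-specified steps.
- **Little depends on it.** The trial stopped in September 2022 after the interim analysis, and the SAP now serves an abbreviated report.

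All of this stands as a limit on size and likelihood. It does not make a constant-variance structure a good first fallback when the plan's own imputation rule pushes variance up at the tested visit.

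**Conclusion.** The point holds conditionally and is minor. The Month 12 standard error may be too small if four things are true: the unstructured model does not converge, some participants die between randomization and Month 12, the imputed 0 is an eGFR value, and survivor variance does not fall over visits. The third is the natural reading and fits the Protocol; setting the change score to 0 would remove the effect.

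Under the assumed values the error is about 11.7–13.6% with SD 16 and even timing, and smaller with SD 20 or early deaths. It is below nominal at 2% deaths if survivor SD declines as in the fourth row. Adding graft loss to the zero rule, as in the Protocol, would increase the number of zeros. An unconditional claim that the standard error is too small goes further than the documents allow.

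**What to change.** In SAP 2.5.1, replace the compound-symmetry step with a structure that allows visit-specific variances, such as heterogeneous Toeplitz or heterogeneous compound symmetry, followed by Month 12 ANCOVA. A simpler option is to go directly from the unstructured model to Month 12 ANCOVA, which also matches the description of the test in SAP 2.5.2. If any structured covariance is kept, report a sandwich standard error with a small-sample correction. SAP 2.5.3 should also say that the imputed 0 is eGFR and not change, and should agree with SAP 3.3 on graft loss.

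The cost is SAP wording only. Heterogeneous structures and sandwich estimates give slightly less precise or less stable standard errors with 32–48 participants per arm. ANCOVA drops participants with no Month 12 value, which matters more after early termination.
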